9.3. Statistical Size Calculations

This is a pilot study and the sample sizes may be insufficient to test the hypothesis. However information on the variability of continuous variables measuring the symptoms such as neuropsychiatric inventory score will be used in power calculations for a larger study. The choice of 30 cases in each arm of the pilot study is a rule of thumb advocated by clinical trial researchers (ref Lancaster G.A 2002).

10. ECONOMIC EVALUATION

The main objective of the economic evaluation of this pilot cluster randomised trial is to rehearse the methods for a definitive evaluation and perform an exploratory cost-effectiveness analysis of the new assessment and management toolkit compared with the usual care provided for dementia. Within this exploratory economic evaluation we will report costs to the NHS, PSS, and patients and carers as well as cost per quality adjusted life year (QALY) with QALYs based on generic (EQ-5D, proxy EQ-5D) and condition specific health state utilities (DEMQOL, DEMQOL- proxy).

In terms of health service use, we will use refined tools from those used in WP1 to estimate resource use. The key refinement will be to tailor the data collection tools to ensure the capture of health service, personal social services and costs falling on patients and carers in the most parsimonious way. Using the same methods used in WP1 we will estimate relevant unit costs. The resource data will be collected within the trial at baseline, 3 and 6 months based on the Case Report Forms (CRF) of the trial.

In addition to the use of health services, at the end of the trial (6 months) we will seek to elicit the costs of administering the tool. This will involve the completion of a structured questionnaire by a small sample of practitioners asking about the time, travel and material involved in the process of using the toolkit.

As far as the patients' quality of life (QoL) is concerned, this will be derived from the responses of the participants to the EQ-5D (or the responses of the carer to a proxy version the EQ-5D for those patients that are incapacitated) and the 28-item DEMQOL in combination with the carer responses to the 31-item DEMQOL-proxy questionnaires, which will be administered at baseline, 3 months and 6 months to the patients and carers, respectively. The data collected will then be converted using the appropriate algorithms in order to generate the generic (EQ-5D) and dementia specific (DEMQOL) utilities of the different health states of LDB. On the other hand, the health related quality of life of the carer will be measured using the carer responses to the EQ-5D administered at the three time points. QALYs will be estimated by using the 'area under the curve' approach for each trial participant and carer (Morris et al, 2007 [1]). The derived QALYs from each questionnaire (i.e. EQ-5D and proxy EQ-5D; patient and carer EQ-5D; DEMQOL (with missing data replaced by DEMQOL-proxy; and DEMQOL-proxy) will then be compared and used for the cost-effectiveness analysis of the study.

Mean costs and mean QALYs will be calculated for each trial intervention and based on them, the incremental cost-effectiveness ratio (ICER) will be calculated. One- and/or multiple-way sensitivity analyses will be conducted to explore uncertainties (alternative utility measures, alternative unit costs, changes in study perspective etc.). In addition to this, stochastic analysis will be conducted to explore the statistical imprecision surrounding estimates of costs, QALYs and ICERs. This analysis will be presented as cost-QALY plots and cost effectiveness acceptability curves (CEACs).

If the intervention is more effective but more costly we will explore the impact of extrapolating from trial findings using data from the literature on effectiveness of treatments.

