3.2. Outcome Measures

Outcome measures:

- Symptom measurement (reduced Neuropsychiatric Inventory (NPI) score; lower unified Parkinson's disease rating scale score; lower Cornell depression score, Geriatric Depression Scale)
- Patient quality of life (patient EQ-5D-5L and carer proxy EQ-5D-5L for incapacitated patients; patient DEMQOL and carer DEMQOL-proxy scales)
- Carer stress and quality of life (carer EQ-5D-5L; HADS; and Zarit burden scale)
- Time spent caring for the person with dementia
- Changes in management (including changes in prescribed medication)
- Rates of cognitive decline (MMSE; and MoCA)
- Global outcomes (observer and carer rated)
- Health economic measures:
 - Primary and secondary health care resource use, use of personal social services
 - Cost to primary and secondary health care and personal social services
 - Patient costs (time and travel costs of accessing health care services)
 - Unpaid costs to carers based on the time spent caring for the person with dementia
 - Patient quality adjusted life years (QALYs) estimated from patient responses to the EQ-5D-5L and DEMQOL, and carer responses to proxy EQ-5D-5L and the DEMQOL-proxy measures, respectively
 - Carer QALYs estimated from carer responses to a carer's EQ-5D-5L

- Incremental cost per QALY gained calculated from the total costs and QALYs of the patient and the carer in order to compare the new assessment and management toolkit with usual care

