7.3. Randomisation

Participating services will be randomised to administer either the management toolkit (intervention arm) or continue with usual care services (control arm). Randomisation will be done using computer generated randomisation at a service level, stratified by site (North East and East Anglia).

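### Section 10 builds the ICER from arm means of costs and area-under-curve QALYs, naming no baseline adjustment and no allowance for randomised services

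*Protocol*

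**What the plan says.** **QALYs.** Protocol section 10 states: "QALYs will be estimated by using the 'area under the curve' approach for each trial participant and carer". The utility questionnaires are "administered at baseline, 3 months and 6 months to the patients and carers".

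**ICER.** Section 10 continues: "Mean costs and mean QALYs will be calculated for each trial intervention and based on them, the incremental cost-effectiveness ratio (ICER) will be calculated". Section 3.2 adds that the ratio covers both members of the pair: "Incremental cost per QALY gained calculated from the total costs and QALYs of the patient and the carer".

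**Uncertainty.** Section 10 says that "stochastic analysis will be conducted to explore the statistical imprecision surrounding estimates of costs, QALYs and ICERs", shown as cost-QALY plots and acceptability curves. It gives neither the method nor the resampling unit. The sensitivity analyses are to "explore uncertainties (alternative utility measures, alternative unit costs, changes in study perspective etc"; the list is open, but baseline adjustment and clustering are not on it.

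**Design.** Section 7.3: "Randomisation will be done using computer generated randomisation at a service level, stratified by site (North East and East Anglia". Section 5 plans at least 8 services. Section 7.1.1 has patients identified and approached at participating services, and allows the baseline visit to fall after the toolkit is first used. Section 7.5 notes that the clinical teams know the allocation.

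**Other models.** Section 9.2.2 plans a linear mixed model for the three visits. It names no service term and is not linked to costs or QALYs.

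**Label.** Section 10 intends to "perform an exploratory cost-effectiveness analysis of the new assessment and management toolkit compared with the usual care provided for dementia". The Trial Summary, 3.1 and 3.2 use the same double label. Section 4 randomises services to the management toolkit alone, and 6.1 requires an LBD diagnosis already on record.

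**The concern.** Baseline utility is the first point of each participant's curve, and it also predicts the 3- and 6-month values. An arm that starts higher will therefore tend to show more QALYs with no effect of the toolkit. The same reasoning applies to costs, where baseline resource use predicts later use.

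The design makes such gaps more likely than in an individually randomised trial of this size. Few units are randomised, and patients enter afterwards through services whose clinicians know their arm. The sign of a small incremental QALY, and with it the ICER and the acceptability curve, could then reflect the starting point.

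Clustering is a second and separate matter. If the stochastic analysis resampled patients as though independent, the plots and curves would look more certain than the data allow.

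The label matters because a cost-effectiveness statement about an assessment tool cannot come from a comparison in which only management was randomised.

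**Working it through.** **1. The plan's own figure.** 30 per arm × 2 arms × 2 parts = 120 patients; with one carer each, 240. This agrees with the Trial Summary. The protocol gives no utility SD, correlation, ICC or cost figure, so the values below are assumptions shown over a range.

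**2. QALY weights.** With visits at 0, 0.25 and 0.5 years, the trapezoid rule gives

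QALY = 0.125 × u0 + 0.25 × u3 + 0.125 × u6.

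The weights sum to 0.5, and baseline holds 0.125 / 0.5 = 25%.

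**3. Carry-over of a baseline gap d.** Let rho be the correlation of baseline with each later utility, with equal SDs. The expected gap at 3 and 6 months is rho × d, so the expected QALY difference with no true effect is

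0.125d + (0.25 + 0.125) × rho × d = (0.125 + 0.375 × rho) × d.

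| rho | factor | d = 0.05 | d = 0.10 |
|---|---|---|---|
| 0 (direct part only) | 0.125 | 0.0063 | 0.0125 |
| 0.5 | 0.3125 | 0.0156 | 0.0312 |
| 0.7 | 0.3875 | 0.0194 | 0.0387 |
| 1 (full persistence) | 0.5 | 0.025 | 0.050 |

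Simulation with no true effect (4,000 runs per setting) gave slopes of 0.31 to 0.32 at rho 0.5 and 0.38 to 0.39 at rho 0.7, in line with the formula. Because patient and carer QALYs are summed, gaps of 0.05 in the same direction in both would add 2 × 0.0156 = 0.031 to 2 × 0.0194 = 0.039; gaps in opposite directions would offset.

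**4. Is a gap of 0.05 unusual?** The SE of the baseline difference is SD × sqrt((2/60) × DEFF), with DEFF = 1 + (m − 1) × ICC and 60 patients per arm. For 8 services, m = 120/8 = 15.

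| SD | ICC 0 | ICC 0.05 | ICC 0.10 |
|---|---|---|---|
| 0.20 | 0.037 | 0.048 | 0.057 |
| 0.25 | 0.046 | 0.060 | 0.071 |
| 0.30 | 0.055 | 0.071 | 0.085 |

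At SD 0.25 and ICC 0.05, a gap of 0.05 is 0.05 / 0.0595 = 0.84 of one SE. If there are 16 services (m = 7.5), the SE is 0.0456 × 1.151 = 0.053, and the gap is still below one SE.

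**5. What baseline adjustment gains.** In the simulation with 8 services of 15, SD 0.25 and ICC 0.05, the SD of the estimated QALY difference fell from 0.0252 to 0.0166 at rho 0.5 (34% lower) and from 0.0269 to 0.0140 at rho 0.7 (48% lower).

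**6. Coverage if services are ignored.** Coverage of a nominal 95% interval = 2 × Phi(1.96 / sqrt(DEFF)) − 1.

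| ICC | 8 services: DEFF | coverage | 16 services: DEFF | coverage |
|---|---|---|---|---|
| 0.01 | 1.14 | 93.4% | 1.065 | 94.2% |
| 0.05 | 1.70 | 86.7% | 1.325 | 91.1% |
| 0.10 | 2.40 | 79.4% | 1.65 | 87.3% |

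In the simulation with 8 services, a patient-level test rejected in about 14% of runs at ICC 0.05 and 21% at ICC 0.10. At ICC 0 the rate was 5%, with no baseline adjustment.

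**The case against.** The strongest reply is that section 10 gives a structure and leaves detail to an analysis plan that is not at hand. Arm means can be taken from a regression, the sensitivity list is open, and covariates and resampling units are often fixed elsewhere. The analysis is called exploratory, the pilot admits in 9.3 that its sample may be too small, and no decision rule hangs on the ICER.

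Much of this stands, and it limits what may be claimed:

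- A reader might infer that the protocol prescribes unadjusted means. It does not say so; it only names no adjustment.
- A reader might infer that uncertainty is understated. A stochastic analysis is planned and its method is open, so understatement follows only if patients are treated as independent. Leaving out baseline utility costs precision but does not by itself spoil coverage, as the 5% rejection rate at ICC 0 shows.
- A reader might infer that baseline utility goes unused. It is used, as the first point of the curve; what is missing is its use as a covariate.
- A reader might take 0.025 QALY as the typical distortion from a gap of 0.05. That is the full-persistence case.
- The count of 8 services is one reading. Section 9.1 can be taken to mean 8 for the Parkinson's part alone, hence the 16-service columns.

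Adjustment also has a difficulty of its own. Section 7.1.1 lets baseline follow first use of the toolkit, so it could remove part of an early effect.

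What does not stand is the appeal to exploratory status. Section 10 gives rehearsal of the definitive methods as a main objective, so the estimator written here is the one likely to be carried forward. That estimator is stated, and a better one uses data already planned.

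On the label, 3.1 also describes the economic aim as concerning the management toolkit alone. That softens the inconsistency but leaves it in place.

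**Conclusion.** The point holds in limited form. The stated route to the ICER lets a baseline utility gap into the incremental QALY, and in this design a gap of 0.05 is ordinary (within about one SE at an assumed utility SD of 0.25). The expected distortion from such a gap is about 0.016 to 0.019 QALY per person at rho 0.5 to 0.7, up to 0.025. These figures rest on equal SDs at the three visits and on assumed values of SD and rho. The cost side has the same weakness but cannot be sized from the documents.

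The clustering part is conditional: coverage of about 87% (8 services) or 91% (16 services) at an assumed ICC of 0.05 applies only if the stochastic analysis ignores services. The label conflict is a matter of wording. None of this threatens the pilot's feasibility aims; the main harm would be rehearsing a weaker method for the definitive trial. The change is recommended.

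**What to change.** 1. In section 10, state that incremental QALYs come from a regression on arm with baseline utility and the region stratum, and incremental costs from one with baseline cost and region. Treat carer QALYs in the same way, with the carer's own baseline.
2. Report the unadjusted differences alongside, giving as the reason that baseline may follow first toolkit use.
3. Base the cost-QALY plots and acceptability curves on a method that respects services and keeps costs and QALYs paired, such as resampling whole services or a service random effect. Acknowledge that either is fragile with few clusters: 8 services leave only 8 − 2 = 6 degrees of freedom between services within arms. Keep the models simple for that reason.
4. In the Trial Summary, 3.1, 3.2 and section 10, name the comparison as management toolkit versus usual care.

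**Cost.** A few sentences and some extra analysis code. Utilities and resource use are already collected at baseline, so no new data are needed. The acceptability curves may show more uncertainty once services are respected, while baseline adjustment should recover some precision.

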11. DATA HANDLING

11.1. Data Collection Tools and Source Document Identification

Data will be collected on paper Case Report Forms by the study team at each participating service. It will then be entered on to a secure validated system with an auditable data trail.

11.2. Data Handling and Record Keeping

Each participant will be allocated a unique identification number when they are enrolled into the study and all subsequent records will be identified using this number.

Data will be handled, computerised and stored in accordance with the Data Protection Act 1998. No participant identifiable information will leave the hospital site. All original consent forms will be held in the ISF, with a copy in the clinical notes and a copy given to the participant. Caldicott approval will be obtained as part of local NHS permission from each site to enable the collection of personal identifiable information as part of this trial. The quality and retention of study data will be the responsibility of the CI. All study data will be retained in accordance with the latest Directive on GCP (2005/28/EC) and local policy.

11.3. Access to Data

The trial economist and/or statistician will only need access to anonymised data. Members of the study team will have access to patient identifiable data and access to study data. Anonymised data will be shared with other researchers and research groups, including the Dementia Platform UK, but within and outside of the EU. This will be included in the participant consent forms.

12. ETHICAL AND REGULATORY CONSIDERATIONS

12.1. Research Ethics Committee Review and Reports

The NCTU will obtain a favourable ethical opinion from an NHS Research Ethics Committee (REC) prior to the start of the trial. All parties will conduct the trial in accordance with this ethical opinion. Local approvals will be sought before any recruitment may commence.

Information sheets will be provided to all eligible participants and written informed consent obtained prior to any data collection for the study. All participants will be given a copy of their signed consent form.

The CI and Project Manager will notify the REC of all required substantial amendments to the trial and those non-substantial amendments that result in a change to trial documentation (e.g. protocol or participant information sheet). Substantial amendments that require a REC favourable opinion will not be implemented until such opinion is obtained. The CI and Project Manager will notify the REC of any serious breaches of GCP or the protocol, urgent safety measures or USARs that occur during the trial.

An annual progress report will be submitted each year to the REC by CI and Project Manager until the end of the trial. This report will be submitted within 30 days of the anniversary date on which the original favourable ethical opinion was granted.

The CI and Project Manager will notify the REC of the early termination or end of trial in accordance with the required timelines.

12.2. Peer Review

Peer review was undertaken by the study funder as part of the overall work package. The sponsor has confirmed that no further peer review will be required. Peer review will also be undertaken as part of the NIHR portfolio adoption process.

12.3. Public and Patient Involvement

The management toolkit was first developed in work package 3, using a Delphi panel of more than twenty national and international multi-disciplinary experts in LBD management. The proposed content of the management toolkit was reviewed in two PPI workshops attended by patients and carers affected by LBD which resulted in the addition of information on general principles.

[name] is a lay co-applicant on this proposal. He has and will continue to provide PPI input to the programme at all stages and is a member of the overall study steering group. The programme is additionally supported by a PPI group comprising three people with experience of PD and/or LBD in

addition to [name]. This PPI group meets as required to provide advice and support to the programme team.

12.4. Regulatory Compliance

The trial will be conducted in accordance with the Research Governance Framework or current (equivalent) regulation. Before any site can enrol patients into the trial, that study must have received all appropriate regulatory approvals and have been assessed for local capacity.

12.5. Protocol Compliance

Prospective, planned deviations or waivers to the protocol are not allowed under the UK regulations on Clinical Trials and must not be used.

12.6. Notification of Serious Breaches to GCP and/or the Protocol

A serious breach is a breach which is likely to effect to a significant degree –

- (a) the safety or physical or mental integrity of the subjects of the trial; or
- (b) the scientific value of the trial

The sponsor must be notified immediately of any incident that may be classified as a serious breach. The CI will notify the NHS REC within the required timelines in accordance with the Sponsor SOP.

12.7. Data Protection and Patient Confidentiality

Personal data will be regarded as strictly confidential. To preserve anonymity, any data leaving the sites will identify participants by their initials and a unique study identification code only. The study will comply with the Data Protection Act, 1998. All study records and Investigator Site Files will be kept at site in a locked filing cabinet with restricted access.

Patient initials, hospital number and date of birth will be collected and recorded at site in order to prevent entry of duplicate participants to the study. Consent will be obtained for this information to be collected at sites. Identifiable information will also be obtained for the study team to contact participants during the study. All information will be used only for the stated purpose(s) and then securely destroyed at site at the end of the study.

12.8. Indemnity

Conduct

The Sponsor has liability for clinical negligence that harms individuals toward whom they have a duty of care. NHS Indemnity covers NHS staff and medical academic staff with honorary contracts conducting the trial for potential liability in respect of negligent harm arising from the conduct of the study at site.

Management

NTW is Sponsor and through the Sponsor, NHS indemnity is provided in respect of potential liability and negligent harm arising from study management.

Design

Indemnity in respect of potential liability arising from negligent harm related to study design is provided by NHS schemes for those protocol authors who have their substantive contracts of employment with the NHS and by Newcastle University Insurance schemes for those protocol authors who have their substantive contract of employment with the University. This is a non-commercial study and there are no arrangements for non-negligent compensation.

Payment

No payment will be given to participants for taking part in the trial. All participants who have their study visits at clinic will be reimbursed for reasonable travel and out of pocket expenses. They will be fully supported throughout study and thanked for their time.

12.9. Amendments

It is the responsibility of the Research Sponsor to determine if an amendment is substantial or not and study procedures must not be changed without the mutual agreement of the CI, Sponsor and the Trial Management Group.

Substantial amendments will be submitted to the REC and will not be implemented until this approval is in place. It is the responsibility of the CI and Project Manager to submit substantial amendments.

Non-substantial amendments may be made at any time with a record of the amendment held in the Trial Master File. Any non-substantial amendment that requires an update to the trial documentation will be submitted to the NHS REC for acknowledgement of the revised version of the document.

Substantial amendments and those minor amendments which may impact sites will be submitted to the relevant NHS R&D Departments for notification to determine if the amendment affects the NHS permission for that site. Amendment documentation will provide to sites by the CI and Project Manager.

14. APPENDICES

14.1. Appendix 2 – Amendment History

Amendment Number	Protocol version no.	Date issued	Author(s) of changes	Details of changes made
1 (Substantial Amendment)	3.0	01.06.16	[name]	
Amendments to the protocol:
 
[name] has replaced [name] as Project Manager and [name] has been added as the Trial Manager. [name] has been added as the lead economist to the signature page.
 
The patient population has been amended to include reference to the patients' carers as this was not clear previously. The total sample size has also been added as this refers to the 60 DLB patients and their carers and the 60 PDD patients & their carers. The combined total of patients and carers is 240.
 
Reference to the Falls diary document and adverse events have been removed from the protocol as these will not be recorded for this study.
 
Reference to the Kings Hallucination Scale has been removed from the protocol as this scale will not be used.
 
The version of the validated questionnaire EQ5D has been specifically stated as EQ-5D-5L in the protocol on pages 17, 22, 23 & 24. This is the version that will be used in the study.

				
The questionnaires relating to the researcher have been added to the schedule of events.
 
The global outcome scale (carer version) has been renamed ‘Baseline Global outcome scale (regarding patient)’.
 
The global outcome scale (patient version) has been removed from the list of patient questionnaires, renamed ‘global outcome scale (regarding patient)’ and added to the informant/carers list of questionnaires.
 
The procedure for those patients who lose capacity during the study has been updated. The research team would seek a consultee rather than remove the patient from the study should they lose capacity during the study. This has also been amended on the IRAS Form (A35).
 
The clinician toolkit use questionnaire may be sent in either paper or electronic format to the clinician and so this has been stated in the protocol.
 
Amendments to Questionnaires:
 
The 2 health economics questionnaires have been amended as per description below.
 
Time and Travel Questionnaire - Further instruction as to how to calculate the distance travelled has been added to Questions A6, A7, C6 & C7
 
Use of Healthcare and Social Services- The wording has been altered in questions A1, A2, A3 & C1. A box has been added to table in Questions B1, B2, B3 & B4 to indicate whether the service stated was NOT used. Question C4 has been added to give the participant the option to opt out of answering questions relating to their income.

--	--	--	--	---

				
Question D1 referring to the patients medication profile has been removed from the new version of the questionnaire. Questions I to K have been removed from this questionnaire.
 
Other: An information document for practitioners has been produced by the trial team.
 
Two Trusts have been added to the list of research sites in the IRAS form as listed below: City of Sunderland Hospitals NHS Foundation Trust Ipswich Hospitals NHS Foundation Trust.

2.0 (minor amendment)	3.0	30.06.16	[name]	
Minor amendment made to the coding in ‘Time and Travel’ and ‘Use of Health and Personal Social Services’ questionnaires. Instead of yes = 1 and no = 2 as written in the old version, the new version states now yes = 1 and no = 0. Don’t know was changed to be recorded as 555 rather than the next sequential number.

3.0 (minor amendment)	4.0	19.10.2016	[name]	
Amendments to the protocol:
 
[name] has replaced [name] as Project Manager. Her details have been added to the Key Contacts on page 4.
 
The frequency of the Clinician Toolkit Feedback Questionnaire has been amended on pages 26 & 28. The Clinicians randomised to receive the management toolkit will now be asked to complete the questionnaire at two time points (approximately 6 months post randomisation and at study end).
 
Amendments to the Clinician Toolkit Questionnaire: The Questionnaire has been updated to reflect the changes in frequency that it will be completed and to make it more general about the clinicians’ view of the toolkit, so incorporating all patients who have been managed rather than per patient.

10.0 (minor amendment)	5.0	07.06.2018	[name]	Amendments to the protocol: [name] has replaced [name] as Trial Statistician. His details have been added to the Signature page on pg. 3 and the key trial contacts on pg. 6.

{Enter all amendments to the protocol here whether substantial or non-substantial. Substantial amendments will require approval by the NHS REC. Non-substantial amendments should be sent to the NHS REC for acknowledgement only}
